8.1.1.1 Clinician-Administered PTSD Scale for DSM-5 (CAPS-5)

The CAPS-5 is a 30-item structured interview that can be used to make current (past month) diagnosis of PTSD, make lifetime diagnosis of PTSD, or assess PTSD symptoms over the past week (Weathers et al. 2013a, 2018; see [Appendix 11](#)). For this study the past week version of the CAPS-5 will be used and will be administered by central rater. Items are scored using a 5-point scale, rated from 0 (absent) to

4 (extreme/incapacitating), with a higher overall score indicating a worse outcome. In addition to assessing the 20 DSM-5 PTSD symptoms, questions asked target the onset and duration of symptoms, subjective distress, impact of symptoms on social and occupational functioning, improvement in symptoms since a previous CAPS administration, overall response validity, overall PTSD severity, and specifications for the dissociative subtype (depersonalization and derealization). Responses will be collected by means of free text to understand intensity and frequency of symptoms, which are then used to select a response on a 5-point Likert scale, ranging from 0 (absent) to 4 (extreme/incapacitating). A total score is calculated by summing severity scores for items 1–20, where a higher score corresponds to greater severity of PTSD or presence of PTSD. Symptom cluster severity scores can also be derived by summing the individual item severity scores for symptoms corresponding to a given DSM-5 cluster: Criterion B (items 1–5); Criterion C (items 6–7); Criterion D (items 8–14); and, Criterion E (items 15–20). For each symptom, standardized questions and probes are provided. Administration requires identification of an index traumatic event to serve as the basis for symptom inquiry via the Life Events Checklist for DSM-5 (LEC-5; see Section 8.1.1.4 for more detail). The LEC-5 will be administered prior to the CAPS-5 at screening only. The CAPS was designed to be administered by clinicians and clinical researchers who have a working knowledge of PTSD but can also be administered by appropriately trained paraprofessionals.

The full interview takes 45–60 minutes to administer. In this study, the past week version of the CAPS-5 will be administered remotely by a central assessor. This first CAPS-5 assessment will be administered no more than 7 days prior to the baseline and at Week 6 and Week 12.

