1. As with previous versions of the CAPS, CAPS-5 symptom severity ratings are based on symptom frequency and intensity, except for items 8 (amnesia) and 12 (diminished interest), which are based on amount and intensity. However, CAPS-5 items are rated with a single severity score, in contrast to previous versions of the CAPS which required separate frequency and intensity scores for each item that were either summed to create a symptom severity score or combined in various scoring rules to create a dichotomous (present/absent) symptom score. Thus, on the CAPS-5 the clinician combines information about frequency and intensity before making a single severity rating. Depending on the item, frequency is rated as either the number of occurrences (how often in the past month) or percent of time (how much of the time in the past month). Intensity is rated on a four-point ordinal scale with ratings of *Minimal*, *Clearly Present*, *Pronounced*, and *Extreme*. Intensity and severity are related but distinct. Intensity refers to the strength of a typical occurrence of a symptom. Severity refers to the total symptom load over a given time period, and is a combination of intensity and frequency. This is similar to the quantity/frequency assessment approach to alcohol consumption. In general, intensity rating anchors correspond to severity scale anchors described below and should be interpreted and used in the same way, except that severity ratings require joint consideration of intensity and frequency. Thus, before taking frequency into account, an intensity rating of *Minimal* corresponds to a severity rating of *Mild / subthreshold*, *Clearly Present* corresponds with *Moderate / threshold*, *Pronounced* corresponds with *Severe / markedly elevated*, and *Extreme* corresponds with *Extreme / incapacitating*.
2. The five-point CAPS-5 symptom severity rating scale is used for all symptoms. Rating scale anchors should be interpreted and used as follows:
 - 0 **Absent** The respondent denied the problem or the respondent's report doesn't fit the *DSM-5* symptom criterion.
 - 1 **Mild / subthreshold** The respondent described a problem that is consistent with the symptom criterion but isn't severe enough to be considered clinically significant. The problem doesn't satisfy the *DSM-5* symptom criterion and thus doesn't count toward a PTSD diagnosis.

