 - 2 **Moderate / threshold** The respondent described a clinically significant problem. The problem satisfies the *DSM-5* symptom criterion and thus counts toward a PTSD diagnosis. The problem would be a target for intervention. This rating requires a minimum frequency of *2 X month or some of the time (20-30%) PLUS* a minimum intensity of *Clearly Present*.
 - 3 **Severe / markedly elevated** The respondent described a problem that is well above threshold. The problem is difficult to manage and at times overwhelming, and would be a prominent target for intervention. This rating requires a minimum frequency of *2 X week or much of the time (50-60%) PLUS* a minimum intensity of *Pronounced*.
 - 4 **Extreme / incapacitating** The respondent described a dramatic symptom, far above threshold. The problem is pervasive, unmanageable, and overwhelming, and would be a high-priority target for intervention.
3. Use the scoring grid on the next page to determine the appropriate severity score for each CAPS-5 item. Start on the left side of the grid with the row corresponding to your intensity rating. Then follow the row that corresponds to the reported frequency to determine the severity score. For example, if your intensity rating is *Pronounced*, and the reported frequent is 2 x week, the corresponding severity score would be *Severe / markedly elevated*. However, if your intensity rating is *Pronounced*, but the reported frequency is 10%, then the corresponding severity score would be *Moderate / threshold*.

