Appendix 11: Clinical Outcome Assessment Instruments

CAPS-5 Past Week Scoring Rules			
INTENSITY	FREQUENCY (# of times or %)		SEVERITY
Minimal	1x/week or more	1-100%	1 = Mild / subthreshold
Clearly Present		1-19%	1 = Mild / subthreshold
	1x/week or more ^a	20-100%	2 = Moderate / threshold
Pronounced	1x/week only ^a	1-49%	2 = Moderate / threshold
	2x/week or more ^b	50-100%	3 = Severe / markedly elevated
Extreme	1x/week only ^a	1-19%	2 = Moderate / threshold
	At least 2x/week but not daily/almost every day ^b	20-79%	3 = Severe / markedly elevated
	Daily/almost every day ^c	80-100%	4 = Extreme / incapacitating

^aFor D1: 1-2 important parts ^bFor D1: several important parts ^cFor D1: most/all important parts

4. You need to establish that a symptom not only meets the DSM-5 criterion phenomenologically, but is also functionally related to the index traumatic event, i.e., started or got worse as a result of the event. CAPS-5 items 1-8 and 10 (reexperiencing, effortful avoidance, amnesia, and blame) are inherently linked to the event. Evaluate the remaining items for trauma-relatedness (TR) using the TR inquiry and rating scale. The three TR ratings are:
 - a. **Definite** = the symptom can clearly be attributed to the index trauma, because (1) there is an obvious change from the pre-trauma level of functioning and/or (2) the respondent makes the attribution to the index trauma with confidence.
 - b. **Probable** = the symptom is likely related to the index trauma, but an unequivocal connection can't be made. Situations in which this rating would be given include the following: (1) there seems to be a change from the pre-trauma level of functioning, but it isn't as clear and explicit as it would be for a *Definite*; (2) the respondent attributes a causal link between the symptom and the index trauma, but with less confidence than for a rating of *Definite*; (3) there appears to be a functional relationship between the symptom and inherently trauma-linked symptoms such as reexperiencing symptoms (e.g., numbing or withdrawal increases when reexperiencing increases).

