 - c. **Unlikely** = the symptom can be attributed to a cause other than the index trauma because (1) there is an obvious functional link with this other cause and/or (2) the respondent makes a confident attribution to this other cause and denies a link to the index trauma. Because it can be difficult to rule out a functional link between a symptom and the index trauma, a rating of *Unlikely* should be used only when the available evidence strongly points to a cause other than the index trauma. NOTE: Symptoms with a TR rating of *Unlikely* should not be counted toward a PTSD diagnosis or included in the total CAPS-5 symptom severity score.
5. **CAPS-5 total symptom severity score** is calculated by summing severity scores for items 1-20. NOTE: Severity scores for the two dissociation items (29 and 30) should NOT be included in the calculation of the total CAPS-5 severity score.
6. **CAPS-5 symptom cluster severity scores** are calculated by summing the individual item severity scores for symptoms contained in a given DSM-5 cluster. Thus, the Criterion B (reexperiencing) severity score is the sum of the individual severity scores for items 1-5; the Criterion C (avoidance) severity score is the sum of items 6 and 7; the Criterion D (negative alterations in cognitions and mood) severity score is the sum of items 8-14; and the Criterion E (hyperarousal) severity score is the sum of items 15-20. A symptom cluster score may also be calculated for dissociation by summing items 29 and 30.
7. **PTSD diagnostic status** should be evaluated with the PAST MONTH version of the CAPS-5. This PAST WEEK version of the CAPS-5 should be used only to evaluate PTSD symptom severity over the past week.

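### Does Section 8.1.1.1 misdefine the CAPS-5 total by leaving out the form's exclusion of symptoms judged unlikely to be trauma-related?

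*Combined protocol and SAP*

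**What the plan says.** Section 8.1.1.1 describes the CAPS-5, refers to Appendix 11 for the instrument, and gives the total in one sentence: "A total score is calculated by summing severity scores for items 1–20". Cluster scores are described in the same way, as sums of item severities. Section 9.4.2 builds the primary endpoint on this total (Week 12 value minus baseline value) and adds no scoring detail.

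The scoring rules of the appended Past Week form (Appendix 11, A11-1) say more:

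- Rule 4 adds a requirement beyond severity: "You need to establish that a symptom not only meets the DSM-5 criterion phenomenologically, but is also functionally related to the index traumatic event".
- It exempts some items: "CAPS-5 items 1-8 and 10 (reexperiencing, effortful avoidance, amnesia, and blame) are inherently linked to the event". For the others: "Evaluate the remaining items for trauma-relatedness (TR) using the TR inquiry and rating scale".
- Rule 4c says that symptoms rated Unlikely "should not be counted toward a PTSD diagnosis or included in the total CAPS-5 symptom severity score".
- Rule 5, which comes next, says the total "is calculated by summing severity scores for items 1-20".

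The form's instructions treat standard scoring as essential, and Section 8.10.1 requires clinicians to complete the official version of each clinician-rated instrument.

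**The concern.** The CAPS-5 total at Week 12 is the primary endpoint, the Week 6 total and the cluster scores are exploratory endpoints, and one interview should yield one score. Section 8.1.1.1 carries over rule 5 but not rule 4c.

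The form also makes it possible for the omission to matter. Under rule 1, "the clinician combines information about frequency and intensity before making a single severity rating", and rule 3 says: "Use the scoring grid on the next page to determine the appropriate severity score for each CAPS-5 item". That grid takes no input on trauma-relatedness, so an item can in principle hold a non-zero severity and a rating of Unlikely. The form's summary sheet has no column for trauma-relatedness and simply adds the four cluster subtotals. The introduction to Appendix 11 warns that the device display may differ from the printed form. If one programmer followed the sentence in 8.1.1.1 and another followed rule 4c, they could derive different primary-endpoint values from the same data.

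**Working it through.** The plan gives no figure to reproduce here. The check has three parts.

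**1. Which items are in scope.** Rule 4 exempts items 1–8 and 10. Items 1–20 without these leave 9 and 11–20, which is 11 items. By cluster, using the item ranges in Section 8.1.1.1 and 4 points per item:

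| Cluster | Items | Rated for trauma-relatedness | Points in scope |
|---|---|---|---|
| B | 1–5 | 0 of 5 | 0 of 20 |
| C | 6–7 | 0 of 2 | 0 of 8 |
| D | 8–14 | 5 of 7 (9, 11–14) | 20 of 28 |
| E | 15–20 | 6 of 6 | 24 of 24 |
| Total | 1–20 | 11 of 20 | 44 of 80 |

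This is the reach of the rule. It is not an effect.

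**2. What the two readings do to one item.** Let s0 and s12 be the severities (0–4) at baseline and Week 12, and let u0 and u12 equal 1 if the item is rated Unlikely at that visit and 0 otherwise.

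- Plain-sum change: s12 − s0.
- Rule 4c change: (1 − u12)·s12 − (1 − u0)·s0.
- Plain sum minus rule 4c: u12·s12 − u0·s0.

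The difference is therefore:

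- Unlikely at baseline only: −s0, from −4 to 0.
- Unlikely at Week 12 only: +s12, from 0 to +4.
- Unlikely at both: s12 − s0, from −4 to +4, and 0 if severity is unchanged.

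Examples:

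- With s0 = s12 = 3, the plain sum gives 0. Rule 4c gives +3 (baseline only), −3 (Week 12 only) or 0 (both).
- With Unlikely at both visits and severity falling from 3 to 1, the plain sum gives −2 and rule 4c gives 0.

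In an arm of 15 (Section 9.2), all observed at Week 12, one severity-3 item rated Unlikely at Week 12 only, in one participant, moves the arm mean by 3/15 = 0.2 points. The same in three participants moves it by 9/15 = 0.6.

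**3. Whether the protocol leaves the rule open.** Set side by side, Section 8.1.1.1 and rule 5 give the same instruction in nearly the same words. Rule 5 does not restate rule 4c either; it relies on the reader having just read it. Section 8.1.1.1 names Appendix 11 as its source, so rule 4c comes in with rule 5. A derivation that stops at the sentence in 8.1.1.1 without opening the cited form departs from the protocol.

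Two features of the form also narrow the room for a difference. It reserves Unlikely for cases where the evidence for another cause is strong. And the inquiry asks whether the symptom began or worsened after the event, a historical question whose answer should rarely change between visits.

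**The case for a change.** The best case for a change is that incorporation by reference settles the intended rule but not what has been programmed. Where the form wants a zero it says so (items 1, 8, 10 and 12 among those summed), and it attaches no such instruction to a rating of Unlikely. If every such item were already scored 0, rule 4c would do nothing to the total. Rule 4c names only the total, so the Criterion D and E cluster scores are uncovered, and a total that drops an item while its cluster keeps it would no longer equal B+C+D+E. One sentence would close all of this.

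Part of this stands. A non-zero severity alongside Unlikely is possible, and the cluster rule is not written down. But the form also supports scoring such a symptom 0: its zero anchor covers reports that do not fit the DSM-5 criterion, and Criteria D and E require symptoms that began or worsened after the trauma. In that case the two readings agree. For the clusters, the summary sheet makes the total the sum of the four subtotals, so the natural reading drops the item from both. Those endpoints are exploratory and summarised descriptively. Nothing in the documents suggests that the device or the code ignores rule 4c; the appendix note concerns how the assessments appear on screen.

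A separate slip is real. Sections 8.1.1.2 and 8.1.1.11 call CGI-S and PGI-S 7-point scales, while both forms offer six categories, as does Table 2 for PGI-S. The 7-point description fits the CGI-C and PGI-C forms. If the six options are coded consecutively, no change score or count is affected.

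**Conclusion.** No change to the plan follows. The sentence in Section 8.1.1.1 is a shortened restatement of the form's summation rule. The exclusion of symptoms rated Unlikely is already in the protocol through Appendix 11, the form's call for standard scoring and Section 8.10.1. What is missing is derivation detail of the kind that belongs in a programming specification and that an analyst scoring from the official instrument would supply.

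At most, one item changes one participant's change score by 4 points, and only if a non-zero severity is recorded with Unlikely and the derivation then ignores rule 4c. No arm-mean or between-arm effect can be stated, because the documents give no frequency for Unlikely. Section 9.1 tests no hypothesis, so no error rate or power depends on the point.

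This rests on two assumptions that the documents cannot confirm: that the device records trauma-relatedness as the appended form does, and that the derivation follows the official scoring rules. The CGI-S and PGI-S wording is a clerical slip with no effect on results under consecutive coding.

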8.1.1.2 Clinician-Global Impression of Severity (CGI-S) and Change (CGI-C)

The CGI-S and CGI-C are single items rated by the clinician (Guy 1976; see [Appendix 11](#)). The CGI-S is used to assess the overall severity of PTSD symptoms over the past 7 days, whereas the CGI-C is used to assess change in overall PTSD symptoms from baseline. Each item is rated on a 7-point scale, ranging from 1 (no symptoms/very much improved) to 7 (very severe/very much worse) for the CGI-S and CGI-C, respectively. Clinicians should make a judgment on severity and any changes from baseline based on the totality of information available to them (e.g., insights from the patient captured during the completion of other trial assessments). The assessments will take up to 5 minutes to complete in their entirety. The CGI-S will be collected at baseline, Week 6, and Week 12. The CGI-C will be collected at Week 6 and Week 12.

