8.1.1.11 Patient-Global Impression of Severity (PGI-S) and Change (PGI-C)

The PGI-S and PGI-C are single items rated by the participant that is used to assess the overall severity over the past 7 days or change of PTSD symptoms relative to baseline (see [Appendix 11](#)). Each item is rated on a 7-point scale, ranging from 1 (no symptoms/very much improved) to 7 (very severe/very much worse) for PGI-S and PGI-C, respectively. The assessments will each take approximately 30 seconds to complete. The PGI-S will be collected at baseline, Week 6, and Week 12. The PGI-C will be collected at Week 6 and Week 12.

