8.10 CLINICAL OUTCOME ASSESSMENTS

8.10.1 Data Collection Methods for Clinical Outcome Assessments

For the description of the clinical outcome assessment used in the study see Section 8.1.1.

PRO instruments will be self-administered at the clinic at specified timepoints during the study (see the schedule of activities in Section 1.3). At the clinic, instruments will be administered before the participant receives any information on disease status, prior to the performance of non-PRO assessments, and prior to the administration of study drug.

PRO instruments will be completed through use of an electronic device provided by the Sponsor. The device will be pre-programmed to enable the appropriate instruments to be administered in the correct order at each specified timepoint. The electronic device and instructions for completing the instruments electronically will be provided by the site

staff. The data will be transmitted to a centralized database maintained by the electronic device vendor. The data will be available for access by appropriate study personnel.

During clinic visits, PRO instruments should be administered as outlined below:

- Participants' health status should not be discussed prior to administration of the instruments.
- Sites must administer the official version of each instrument, as provided by the Sponsor. Instruments must not be copied from the protocol.
- Sites should allow sufficient time for participants to complete the instruments, estimated to be approximately 15–30 minutes at baseline, Week 6, and Week 12.
- Sites should administer the instruments in a quiet area with minimal distractions and disruptions.
- Participants should be instructed to answer questions to the best of their ability; there are no right or wrong answers.
- Site staff should not interpret or explain questions, but may read questions verbatim upon request.
- Participants should not obtain advice or help from others (e.g., family members or friends) when completing the instruments.

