ClinRO instruments will be completed at the clinic at specified timepoints during the study (see schedule of activities in Section 1.3). ClinRO instruments will be administered prior to the administration of study drug. The instruments will be completed through use of an electronic device provided by the Sponsor. Clinicians must complete the official version of each ClinRO instrument, as provided by the Sponsor. Instruments must not be copied from the protocol. The data will be transmitted to a centralized database maintained by the electronic device vendor.

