9.4.3.1 Clinician-Global Impression of Severity (CGI-S)

The change from baseline in CGI-S will be calculated as the CGI-S score at Week 12 minus the CGI-S score at baseline. A negative change from baseline in CGI-S indicates improvement.

The count and percentages for each value of CGI-S changes will be evaluated.

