Appendix 10: Examples of Cytochrome P450 3A4 Inducers and Inhibitors

Moderate CYP3A4 Inhibitors	
Amprenavir	Fluconazole
Aprepitant	Grapefruit juice
Atazanavir	Imatinib
Casopitant	Isavuconazole
Cimetidine	Istradefylline
Ciprofloxacin	Lefamulin
Crizotinib	Letermovir
Cyclosporine	Magnolia vine (Schisandra sphenanthera)
Darunavir	Netupitant
Diltiazem	Nilotinib
Dronedarone	Ravuconazole
Duvelisib	Tofisopam
Erythromycin	Verapamil
Faldaprevir	Voxelotor
Fedratinib	

CYP3A4 = cytochrome P450 3A4.

Sourced from <https://www.druginteractionsolutions.org/>.

REFERENCES

Drug Interaction Solutions, University of Washington School of Pharmacy [resource on the internet]. 2020. Available from: <https://www.druginteractionsolutions.org/>.

Appendix 11

Clinical Outcome Assessment Instruments

[figure not shown]
All assessments (except Structured-Clinical Interview for DSM-5 [SCID-5]) will be completed through use of an electronic device. Please note, the assessments shown in this appendix may not be exactly the same as they appear on the electronic device.

TABLE OF CONTENT

A11-1	Clinician-Administered PTSD Scale For DSM-5 (CAPS-5)....	133
A11-2	Clinician-Global Impression of Severity (CGI-S).....	157
A11-3	Clinician-Global Impression of Change (CGI-C).....	158
A11-4	Patient-Health Questionnaire-9 (PHQ-9)	159
A11-5	Life-Events Checklist For DSM-5 (LEC-5)	160
A11-6	PTSD Checklist for DSM-5 (PCL-5).....	162
A11-7	Structured-Clinical Interview for DSM-5 (SCID-5).....	164
A11-8	Beck Anxiety Inventory (BAI)	200
A11-9	Pittsburgh-Sleep Quality Index (PSQI)	201
A11-10	Sheehan Disability Scale (SDS)	203
A11-11	Cognition And Physical Functioning Questionnaire (CPFQ)..	204
A11-12	Patient-Global Impression of Severity (PGI-S).....	205
A11-13	Patient-Global Impression Of Change (PGI-C).....	206
A11-14	Columbia-Suicide Severity Rating Scale (C-SSRS), Baseline	207
A11-15	Columbia-Suicide Severity Rating Scale (C-SSRS), Since Last Visit	210

A11-1 CLINICIAN-ADMINISTERED PTSD SCALE FOR DSM-5 (CAPS-5)

(Sample; Not to Be Used to Enter Subject Data)

**Clinician-Administered PTSD
Scale for *DSM-5* (CAPS-5)
Past Week Version**

Version date: 16 April 2018

Reference: Weathers, F. W., Blake, D. D., Schnurr, P. P., Kaloupek, D. G., Marx, B. P., & Keane, T. M. (2015). *The Clinician-Administered PTSD Scale for DSM-5 (CAPS-5) – Past Week* [Measurement instrument]. Available from <https://www.ptsd.va.gov/>

URL: <https://www.ptsd.va.gov/professional/assessment/adult-int/caps.asp>

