Appendix 11: Clinical Outcome Assessment Instruments

PTSD totals	Past Week	
Totals	Total Sev	Total # Sx
Sum of subtotals (B+C+D+E)	0	0

F. Duration of disturbance	Current
(22)	NOT APPLICABLE

G. Distress or impairment (need 1 for diagnosis)	Past Week	
Criterion	Sev	Cx (Sev \geq 2)?
(23) Subjective distress		0 = NO 1 = YES
(24) Impairment in social functioning		0 = NO 1 = YES
(25) Impairment in occupational functioning		0 = NO 1 = YES
G subtotals	G Sev = 0	#G Cx = 0

Global ratings	Past Week
(26) Global validity	
(27) Global severity	
(28) Global improvement	

Dissociative symptoms (need 1 for subtype)	Past Week	
Symptom	Sev	Sx (Sev \geq 2)?
(29) 1 – Depersonalization		0 = NO 1 = YES
(30) 2 – Derealization		0 = NO 1 = YES
Dissociative subtotals	Diss Sev = 0	#Diss Sx = 0

A11-2 CLINICIAN-GLOBAL IMPRESSION OF SEVERITY (CGI-S)

(Sample; Not to Be Used to Enter Subject Data)

Taking into account all aspects of the individual's PTSD symptoms, please rate how the individual's symptom severity has been during the past 7 days? Do not consider other conditions or comorbidities in your assessment.

- No symptoms
- Very mild
- Mild
- Moderate
- Severe
- Very severe

A11-3 CLINICIAN-GLOBAL IMPRESSION OF CHANGE (CGI-C)

(Sample; Not to Be Used to Enter Subject Data)

Taking into account all aspects of the individual's PTSD symptoms, how much would you rate the change in clinical status since their admission to the study? Do not consider other conditions or comorbidities in your assessment.

- Very much improved
- Much improved
- Minimally improved
- No change
- Minimally worse
- Much worse
- Very much worse

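### Does it matter that the text calls CGI-S a 7-point scale when its sample form has six categories?

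*Combined protocol and SAP*

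**What the plan says.** Section 8.1.1.2 describes both clinician global items in one sentence: "Each item is rated on a 7-point scale, ranging from 1 (no symptoms/very much improved) to 7 (very severe/very much worse) for the CGI-S", and likewise for CGI-C. Section 8.1.1.11 does the same for the patient items: "Each item is rated on a 7-point scale, ranging from 1 (no symptoms/very much improved) to 7 (very severe/very much worse) for PGI-S", and likewise for PGI-C.

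The sample CGI-S form (A11-2) asks for a rating of how "symptom severity has been during the past 7 days". It then lists six answers: no symptoms, then very mild, mild, moderate and severe, up to very severe. No numbers stand beside them. The PGI-S form (A11-12) has the same six, as does the PGI-S endpoint in Table 2. The CGI-C and PGI-C forms each have seven.

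Section 9.4.3.1 defines the endpoint: "The change from baseline in CGI-S will be calculated as the CGI-S score at Week 12 minus the CGI-S score at baseline". It then says: "The count and percentages for each value of CGI-S changes will be evaluated".

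On which form counts, Section 8.10.1 says of clinician instruments: "Clinicians must complete the official version of each ClinRO instrument, as provided by the Sponsor". For patient instruments it says: "Sites must administer the official version of each instrument, as provided by the Sponsor". The introductory note to Appendix 11 warns that "the assessments shown in this appendix may not be exactly the same as they appear on the electronic device".

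**The concern.** CGI-S change at Week 12 is one of two secondary efficacy endpoints, and subtraction needs one number per label. The text fixes only the two ends, 1 and 7. Six labels cannot fill seven codes, so a programmer who took both the form and the end codes literally would have to leave one code between 2 and 6 unused, and nothing says which. A one-category improvement across the gap would then count as 2 points instead of 1, and that participant would move to another row of the change table. With about 15 participants per arm, one such move is 1/15 = 6.7% of a fully observed arm.

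**Working it through.** **Counting levels.** The stated figure is seven.

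| Item | Text | Sample form | Agree? |
|---|---|---|---|
| CGI-C | 7 | 7 | yes |
| PGI-C | 7 | 7 | yes |
| CGI-S | 7 | 6 | no |
| PGI-S | 7 | 6 (also 6 in Table 2) | no |

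The count is right for the change items and wrong for the severity items, and each pair shares one descriptive sentence. The likeliest explanation is that the change item's count was carried over to the severity item. The same six labels appear in three places, so a line lost in text extraction is unlikely.

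**Consecutive codes.** Let label i have code i + c, where c is any constant. A move from label a to label b gives (b + c) − (a + c) = b − a. The constant cancels, so codes 1 to 6, 0 to 5 and 2 to 7 all give the same change for every participant. With k levels the change runs from −(k − 1) to +(k − 1) and takes 2(k − 1) + 1 values:

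- six levels: −5 to +5, 2 × 5 + 1 = 11 values;
- seven levels: −6 to +6, 2 × 6 + 1 = 13 values.

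In both cases a one-category move is 1 point and the table in Section 9.4.3.1 is well defined.

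**Six labels with end codes 1 and 7.** One code from 2 to 6 is unused. If the gap lies between labels j and j + 1, the ordered baseline/Week 12 pairs that cross it number 2 × j × (6 − j), out of 6 × 6 = 36:

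| j | Unused code | Pairs affected |
|---|---|---|
| 1 | 2 | 2 × 1 × 5 = 10 |
| 2 | 3 | 2 × 2 × 4 = 16 |
| 3 | 4 | 2 × 3 × 3 = 18 |
| 4 | 5 | 2 × 4 × 2 = 16 |
| 5 | 6 | 2 × 5 × 1 = 10 |

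Each affected pair differs from consecutive coding by exactly 1 point. For example, very severe to severe is −1 under consecutive codes and −2 if code 6 is the unused one. The sign never changes, because the codes still rise with severity: improved, unchanged and worse are the same under every coding.

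This last case combines the end codes of a seven-level description with the labels of a six-level form. Neither source describes it. The seven-level text implies steps of 1, and the six-option form has no codes.

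**PGI-S.** Table 2 reports proportions by named category, so no numeric code enters the analysis.

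**The case for a change.** The strongest reply is that pointing to the device settles nothing on paper, because the documents give neither its category count nor its codes. Whichever version was deployed, some text is wrong: Sections 8.1.1.2 and 8.1.1.11 if it has six levels, or the sample forms and the Table 2 list if it has seven. The only codes printed do put very severe at 7. And with no test or model planned, the table of change values is the main planned CGI-S output, so its rows ought to be known before lock.

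The wording point stands. The step to a consequence does not. The code list comes with the device data, so whoever programs the table sees the stored values and need not rebuild them from the protocol. Missing numbers on a sample form are not a defect in themselves: the BAI form prints none either, and its 0 to 3 scoring is given in Section 8.1.1.7. Nor do the documents suggest that the coding differs between visits or arms.

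A related question concerns the CAPS-5 total. Section 8.1.1.1 gives a plain sum of items 1 to 20 without repeating the instrument's rule that leaves out symptoms judged unlikely to be trauma-related. That section refers to Appendix 11, where the rule is printed (scoring rule 4c), so the total is already defined. Whether the cluster scores follow the same rule touches only an exploratory endpoint. The documents do not give the frequency of such ratings, so no effect can be sized.

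**Conclusion.** This is a clerical inconsistency in how two severity items are described, and it changes no planned result. Under either coherent reading (six levels coded consecutively, or seven levels with an incomplete sample form) the CGI-S subtraction is defined and each category step counts 1 point. For the six-level device, the size of the discrepancy is zero for every participant. The 10 to 18 of 36 pairs belong to a coding that nothing in the plan calls for. Those pairs are not equally likely and their frequencies are not given, so the counts are not an estimate of error.

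The conclusion assumes that the deployed instrument stores consecutive codes, which the documents do not show. If it did not, the gap would be visible in the code list, the direction of every change would stand, and the effect would be confined to rows of one descriptive table in a study that Section 9.1 says tests no hypothesis. Correcting the category count would tidy the text but would not alter the data collected, the analysis or its interpretation.
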